6.4. Week 2 through Week 44 Assessments

The following assessments will be completed at each visit or as specified. All assessments are summarized in the Study Procedures Table ([Appendix 2](#)).

Subject's Global Assessment, HAQ-DI and Pain Scale, FACIT-Fatigue, and SF-36, are recommended to be completed before any other study procedures. Invasive study procedures such as blood draws should be done at the end of a study visit.

- Subject's global assessment
- HAQ-DI and Pain Scale
- FACIT-Fatigue and SF-36 at Weeks 4, 12, and 24
- WPAI-RA and EQ-5D at Weeks 4, 12, and 24, where available
- **CCI**
- TSQM at Weeks 12, 24 and 36
- Healthcare resource utilization questionnaire at Weeks 12 and 24
- Complete physical examination at Week 24 (symptom-directed physical examination conducted at all other visits)
- Weight
- Vital Signs
- SJC66/TJC68
- Physician's global assessment
- 12-Lead ECG at Weeks 12, 24, and 36
- Assessment of serious AE(s), AE(s) and concomitant medications
- Obtain blood sampling for:
 - Hematology and Serum Chemistry
 - Pre-dose vfpBMC and leukocyte subsets samples at Weeks 4, 8, 12, 24, and 36 (US and Canada only)
 - Lipid profile (fasting) at Weeks 12 and 24
 - Serum CRP
 - Biomarker blood samples at Weeks 4, 8, 12, 24, and 36

— Blood sampling for PK at Weeks 4, 12 and 24

— Quantitative Ig at Week 24

— CCI [REDACTED]

— CCI [REDACTED]

- Urinalysis at Week 24
- Urine stored for biomarker analysis at Weeks 12 and 24
- Urine pregnancy test (for women of childbearing potential, as defined per protocol). During the periods where study visits are every 6-8 weeks, women should continue to have pregnancy tests every 4 weeks, using home pregnancy urine tests, that will be provided to them. The site will call the subject every 4 weeks to obtain results of these pregnancy tests and will record the information in the source documents and CRF.
- Radiographs of hands, wrists, and feet at Weeks 12 and 24
- CCI [REDACTED]
- Carotid artery ultrasounds at Week 24, at selected sites only when and where available

6.5. Week 52/Early Termination (ET)

If a subject discontinues study, every attempt should be made to perform the required study-related ET and Post-Treatment Week 4 visits and procedures.

Subject's Global Assessment, HAQ-DI and Pain Scale, FACIT-Fatigue, and SF-36, are recommended to be completed before any other study procedures. Invasive study procedures such as blood draws should be done at the end of a study visit.

- Subject's global assessment
- HAQ-DI and Pain Scale
- FACIT-Fatigue and SF-36
- WPAI-RA and EQ-5D, where available
- CCI [REDACTED]
- TSQM, when and where available

- Healthcare resource utilization questionnaire
- Complete Physical examination
- Weight
- Vital signs
- SJC66/TJC68
- Physician's global assessment
- 12-Lead ECG
- Obtain blood samples for:
 - Hematology
 - Serum Chemistry
 - Lipid profile (fasting)
 - Serum CRP
 - Pregnancy test (serum required if subject is entering into LTE)
 - Blood sampling for PK
 - Biomarker blood samples
 - Quantitative Ig at Week 24
 - vfpBMC and leukocyte subsets samples (US and Canada only)
 - CCI
- Urinalysis (including pregnancy test if applicable)
- Urine stored for biomarker analysis Assessment of serious AE(s) (S)AE(s) and concomitant medication
- Radiographs of hands, wrists, and feet
- Carotid artery ultrasound, at selected sites only
- Review Entry criteria for LTE (if applicable)

6.6. Post Treatment Week 4

The following procedures will be completed 4 weeks after the subject's last dose of study treatment. This visit is not applicable if subject is continuing onto the LTE study.

- Symptom-driven physical examination
- Weight
- Vital signs
- 12-lead ECG
- Obtain blood samples for:
 - Hematology and Serum Chemistry
- Urinalysis
- Urine Pregnancy test (females of child bearing potential, as defined per protocol)

6.7. Study Assessments

6.7.1. Efficacy

Efficacy assessments will be carried out at Day 1 and at Weeks 2, 4, 8, 12, 14, 16, 20, 24, 26, 32, 36, 40, 48 and 52, or at ET (if applicable).

Analysis of RA data will include the derived ACR (ACR20, 50, 70 as well as ACR-N and EULAR response criteria, DAS28 [CRP], CDAI, and SDAI as well as the individual components of the ACR response criteria [TJC68, SJC66, HAQ-DI, Physician's Global assessment, Subject's Global Assessment, Subject's Assessment of Arthritis Pain and CRP]) and radiographs of hands, wrists and feet (mTSS and mTSS components of erosion score and joint space narrowing).

Additionally subjects will be asked to complete questionnaires, including the FACIT-fatigue scale, SF-36, EQ-5D, WPAI-RA at Day 1 and at Weeks 4, 12, 24, 36, and 52, or at ET (if applicable). Healthcare resource utilization will be assessed at the Day 1 and at Weeks 12, 24, 36, and 52, or at ET (if applicable). The TSQM should be completed on Day 1 and Weeks 12, 24, 36 and 52.

6.7.1.1. Evaluation of Disease Activity: Tender and Swollen Joint Counts

Assessment of tender and swollen joints will take place at the time points indicated in the study procedures table ([Appendix 2](#)).

Each of 68 joints will be evaluated for tenderness and each of 66 joints will be evaluated for swelling (a list of joints to be evaluated is provided in [Appendix 7](#)).

An independent joint assessor with adequate training and experience in performing joint assessments will be designated at each study site to perform all joint assessments, and should be blinded to the other study assessments performed on that day. The joint assessor should preferably be a rheumatologist; however, if a rheumatologist is not available, it should be a health care worker with experience in performing joint assessments. The assessor should remain the same throughout the study per subject, as much as possible. It is required that the designated joint assessor identify an appropriate back up assessor to provide coverage if the designated joint assessor is absent.

6.7.1.2. Subject's Global Assessment of Disease Activity

The Subject's Global assessment of Disease Activity will be performed at the time points indicated in the study procedures table ([Appendix 2](#)). The Subject's Global assessment of Disease Activity should be completed before any other study procedures

The Subject's Global Assessment of Disease Activity will be recorded on a 0-100 mm visual analog scale (VAS), with 0 indicating "no arthritis" and 100 indicating "severe arthritis".

6.7.1.3. Physician's Global Assessment of Disease Activity

The Physician's Global assessment of Disease Activity will be performed at the time points indicated in the study procedures table ([Appendix 2](#)).

The Physician's Global Assessment of Disease Activity will be recorded on a 0-100 mm VAS, with 0 indicating "no disease activity" and 100 indicating "maximum disease activity". The evaluating physician and the subject should complete the global assessments independently of each other.

6.7.1.4. Serum CRP

The subject's serum CRP will be measured at the time points indicated in the study procedures table ([Appendix 2](#)).

6.7.1.5. Health Assessment Questionnaire – Disability Index and Pain Scale

The functional status of the subject will be assessed using the HAQ-DI at the time points indicated in the study procedures table ([Appendix 2](#)) and should be completed before any other study procedures. The HAQ-DI is a 20-question instrument that assesses the degree of difficulty a person has in accomplishing tasks in 8 domains (dressing, arising, eating, walking, hygiene, reaching, gripping and errands/chores). Responses are scored on a 4-point Likert scale from 0, indicating no difficulty, to 3, indicating inability to perform a task in that area. The need for aids or help from another person will also be recorded. The HAQ-DI total score ranges from 0 to 3 with higher scores indicating greater dysfunction.

As part of the HAQ-DI, subjects will be asked to assess their average pain during the last week on a 0-100 mm VAS, with 0 indicating “no pain” and 100 indicating “severe pain”. This assessment should be completed before the joint examination. This pain score will be used to drive the ACR20/50/70.

6.7.1.6. FACIT-Fatigue Scale

The FACIT-Fatigue (version 4) will be completed at the time points indicated in the study procedures table ([Appendix 2](#)) and should be completed before any other study procedures where local language questionnaires are available.

The FACIT-Fatigue scale measures an individual’s level of fatigue during their usual daily activities over the past week. It consists of 13 questions with a 7-day recall period on a 5-point Likert scale, with 0 indicating “not at all” and 4 indicating “very much”. The total score ranges from 0 to 52. Higher scores indicate a better the quality of life .

6.7.1.7. 36-Item Short-form Health Survey

The SF-36 (version 2) will be completed at the time points indicated in the study procedures table ([Appendix 2](#)) and should be completed before any other study procedures.

The SF-36 is a health related quality of life instrument consisting of 36 questions belonging to 8 domains in 2 components and covers a 4-week recall period:

- physical well-being: 4 domains: physical functioning (10 items), role physical (4 items), bodily pain (2 items), and general health perceptions (5 items)
- mental well-being: 4 domains: vitality (4 items), social functioning (2 items), role emotional (3 items), and mental health (5 items).

The remaining item (health transition) is not part of the above domains but is kept separately. These scales will be rescaled from 0 to 100 (converting the lowest possible score to 0 and the highest possible score to 100), with higher scores indicating a better quality of life. The SF-36 is not disease specific and has been validated in numerous health states.

6.7.1.8. EuroQol 5 Dimensions

The EQ-5D questionnaire will be completed at the time points indicated in the study procedures table ([Appendix 2](#)) and should be completed before any other study procedures where local language questionnaires are available.

The EQ-5D is a standard measure of health status developed by the EuroQol Group to provide a simple, generic measure of health for clinical and economical appraisal {[The EuroQol Group 1990](#)}. The EQ-5D is not disease specific and has been validated in numerous health states.

The tool consists of the EQ-5D descriptive system and the EQ VAS. The descriptive part comprises 5 dimensions (mobility, self-care, usual activities, pain/discomfort, and anxiety/depression). Each of these 5 dimensions has 3 levels (no problem, some problems, and severe problems). Results for each of the 5 dimensions are combined into a 5-digit number to describe the subject's health state. The VAS records the subject's health on a 0-100 mm VAS scale, with 0 indicating "the worst health you can imagine" and 100 indicating "the best health you can imagine".

6.7.1.9. Work Productivity and Activity Impairment for Rheumatoid Arthritis

The WPAI-RA is a questionnaire developed to measure impairments in work activities in subjects with RA {Zhang et al 2010} and will be completed at the time points indicated in the study procedures table (Appendix 2) and should be completed before any other study procedures where local language questionnaires are available.

The questionnaire consists of 6 questions (currently employed, work time missed due to RA, Work time missed due to other reasons, hours actually worked, degree RA affected productivity while working [0-10 VAS; with 0 indicating no effect and 10 indicating RA completely prevented the subject from working], and degree RA affected productivity in regular unpaid activities [0-10 VAS; with 0 indicating no effect and 10 indicating RA completely prevented the subject's daily activities]). The recall period for questions 2 to 6 is 7 days.

Four main outcomes (expressed in percentages) can be obtained from the WPAI-RA: percentage of work time missed due to RA, percentage of impairment due to RA, percentage of overall work impairment due to RA, percentage of activity impairment due to RA. Note that for subjects who did not work during the 7 days covered by the WPAI-RA, the percent overall work impairment will be equal to the percent of work time missed due to RA.

6.7.1.10. Healthcare Resource Utilization

The Healthcare Resource Utilization Questionnaire is designed to assess healthcare usage during the previous three months across a number of direct medical cost domains.

This questionnaire should be completed by the patient prior to any procedures being performed at the visit, if possible where local language questionnaires are available.

6.7.1.11. Hands, Wrists, and Feet Radiographs

Hands, wrists, and feet radiographs will be taken at the time points indicated in the study procedures table (Appendix 2). Note that if a subject discontinues the study early and has had X-rays performed in the <12 week period prior to discontinuation, these do not need to be repeated at ET. Radiographs performed after enrollment may be done +/-7 days of the scheduled visit.

All subjects who discontinue from investigational therapy but continue study visits and procedures, should continue to have radiographs performed as outlined in the study procedure table ([Appendix 2](#)).

The radiographs will be evaluated through central review by independent blinded assessors using the mTSS.

6.7.1.12 Exploratory patient reported outcomes

CCI
[REDACTED]

6.7.2. Safety and Tolerability

Adverse events (AEs), physical examinations, vital signs, 12-lead electrocardiograms (ECG) and laboratory assessments (standard hematology, serum/plasma chemistry, , and urinalysis) will be collected.

6.7.3. Treatment Satisfaction Questionnaire for Medication (TSQM)

The TSQM will assess the overall level of satisfaction or dissatisfaction with medication subjects are taking. Subjects will be asked to rate their treatment satisfaction at the time points indicated in the study procedures table ([Appendix 2](#)). The TSQM will implemented when and where local language TSQM are available.

6.7.4. Clinical Laboratory Evaluations

The hematology and serum chemistry laboratory analyses will be performed at a central laboratory. Reference ranges will be supplied by the central laboratory and will be used by the investigator to assess the laboratory data for clinical significance and pathological changes.

Blood samples will be collected by venipuncture (or optional indwelling catheter for pharmacokinetic sampling days) in the arm at the time points indicated in the study procedures table ([Appendix 2](#)). In addition, urine samples for the clinical laboratory assessments will be collected. Subjects only need to be fasted at days were lipid profiling is scheduled.

- Please refer to [Appendix 6](#) for table of Clinical laboratory tests.

The laboratory values outside the normal range will be flagged and clinical relevance will be assessed by the investigator. More frequent sampling as well as additional tests may be performed as deemed necessary by the investigator as indicated.

Note that in the case where clinically significant laboratory test results are a potential reason for discontinuation from the study drug and withdrawal from the study, retesting of the affected parameter(s) should be prompt (within 3 to 7 days) after the investigator has consulted with the medical monitor. A decision regarding subject discontinuation should be made after the results from the retest are available (see Section 3.5 for additional information).

The details of sample handling and shipment instructions will be provided in a separate laboratory manual.

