6.2.2. Day 1 Assessments

At Day 1, after the subject's eligibility for the study has been confirmed, the subject will be randomized into the study to receive one of four study dosing regimens.

Subject's Global Assessment, HAQ-DI and Pain Scale, FACIT-Fatigue, and SF-36 are recommended to be completed before any other study procedures. Invasive study procedures such as blood draws should be done at the end of a study visit. The following will be performed and documented at Day 1 prior to dosing:

- Subject's global assessment
- HAQ-DI and Pain Scale FACIT-Fatigue and SF-36
- WPAI-RA and EQ-5D, where available
- CCI [REDACTED]
- TSQM, when and where available
- Healthcare resource utilization questionnaire
- Symptom-driven physical examination
- Weight
- Vital signs
- SJC66/TJC68
- Physician's global assessment
- Obtain blood samples for:
 - Hematology and Serum Chemistry
 - Lipid profile (fasting)
 - Serum CRP
 - Biomarker blood samples

— Pre-dose vFPBMC and leukocyte subsets samples (US and Canada only)

— CCI [REDACTED]

— CCI [REDACTED]

• CCI [REDACTED]

- Carotid artery ultrasounds, at selected sites only when available
- Urinalysis (including pregnancy test, if applicable)
- Urine stored for biomarker analysis
- Review concomitant medications
- Record any serious adverse events and all adverse events related to protocol mandated procedures occurring after signing of the consent form.

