Appendix 2. Study Procedures Table

EVENT		Screening ^a	Treatment Period														Follow Up ^d
			Day 1 ^b	W2	W4	W8	W12	W14	W16	W20	W24	W26	W30	W36	W44	W52/ ET ^c	Post Treatment Week 4
Visits	Visit window (Days)			(±3 days)	(±3 days)	(±3 days)	(±3 days)	(±3 days)	(±3 days)	(±3 days)	(±3 days)	(±3 days)	(±3 days)	(±7 days)	(±7 days)	(±7 days)	(±7 days)
Screening Assessments	Informed Consent	X															
	Inclusion/Exclusion Criteria	X	X ^e														
	Demographics and Baseline/ Disease Characteristics	X															
	RA diagnosis and Prior RA Treatment, Medical History ^f	X															
	Complete Physical Examination ^g	X									X						X
	TB test and Chest X-ray ^h	X															
	RF/anti-CCP Ab	X															

EVENT		Screening ^a	Treatment Period														Follow Up ^d	
			Day 1 ^b	W2	W4	W8	W12	W14	W16	W20	W24	W26	W30	W36	W44	W52/ ET ^c	Post Treatment Week 4	
Visits	Visit window (Days)		(±3 days)	(±3 days)	(±3 days)	(±3 days)	(±3 days)	(±3 days)	(±3 days)	(±3 days)	(±3 days)	(±3 days)	(±3 days)	(±7 days)	(±7 days)	(±7 days)	(±7 days)	(±7 days)
Patient Questionnaires	Subject's global assessment ⁱ	X	X	X	X	X	X	X	X	X	X	X	X	X	X	X	X	
	HAQ-DI and Pain Scale ⁱ	X	X	X	X	X	X	X	X	X	X	X	X	X	X	X	X	
	FACIT-Fatigue, SF-36, WPAI-RA, EQ-5D ⁱ		X		X		X				X			X		X		
	Healthcare resource utilization questionnaire and TSQM ⁱ		X				X				X			X		X		
CCI																		
Physical Exam and Provider Assessments	Physician's global assessment	X	X	X	X	X	X	X	X	X	X	X	X	X	X	X	X	
	Vital signs ^j	X	X	X	X	X	X	X	X	X	X	X	X	X	X	X	X	X
	Symptom-driven physical examination		X	X	X	X	X	X	X	X		X	X	X	X			X
	12-Lead ECG	X					X				X			X		X		X
	SJC66/TJC68	X	X	X	X	X	X	X	X	X	X	X	X	X	X	X	X	
	Weight	X	X	X	X	X	X	X	X	X	X	X	X	X	X	X	X	X

[figure not shown]
EVENT	Screening ^a	Treatment Period														Follow Up ^d	
		Day 1 ^b	W2	W4	W8	W12	W14	W16	W20	W24	W26	W30	W36	W44	W52/ ET ^c	Post Treatment Week 4	
			(±3 days)	(±3 days)	(±3 days)	(±3 days)	(±3 days)	(±3 days)	(±3 days)	(±3 days)	(±3 days)	(±3 days)	(±7 days)	(±7 days)	(±7 days)	(±7 days)	(±7 days)
Pregnancy test ^k	X	X	X	X	X	X	X	X	X	X	X	X	X	X	X	X	X
Hematology and Chemistry ^l	X	X	X	X	X	X	X	X	X	X	X	X	X	X	X	X	X
Serum CRP	X	X	X	X	X	X	X	X	X	X	X	X	X	X	X	X	
Urinalysis and urine for biomarkers ^m	X	X				X					X					X	X
Quantitative Ig	X										X					X	
Endocrine: FSH, TSH, and HbA1c	X																
Lipid profile (fasting) ¹		X				X					X					X	
CCI																	
PK blood samples ^o				X		X					X					X	

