Appendix 6. Laboratory Assessment Table

Hematology	Chemistry	Urinalysis	Other
Hematocrit Hemoglobin Platelet count Red blood cell (RBC) count Red blood cell indices White blood cell (WBC) count Differentials (absolute and percentage), including: Leukocytes Monocytes Neutrophils Eosinophils Basophils Mean corpuscular volume (MCV)	Alkaline phosphatase Aspartate aminotransferase (AST) Alanine aminotransferase (ALT) Gamma-glutamyl transpeptidase (GGT) Total bilirubin Direct and indirect bilirubin Total protein Albumin Bicarbonate Blood urea nitrogen (BUN) Calcium Chloride CPK Serum creatinine Glucose Phosphorus Magnesium Potassium Sodium Amylase Lipase Uric Acid (screening)	Appearance Blood Color Glucose Specific gravity Nitrites Leukocyte esterase pH Protein Urobilinogen Reflex to microscopic urinalysis if dipstick result is abnormal.	Urine drug screen for: Amphetamines Cocaine Methadone Opiates Leukocyte subsets* vfpBMC* C-reactive protein (hsCRP) Rheumatoid factor and anti-cyclic citrullinated peptide antibody (RF/Anti-CCP) QuantiFERON- TB GOLD Quantitative Ig subclasses at Screening, Week 24 and 52 Only performed at sites that participate in the carotid imaging study at selected sites and where available at Day 1, Week 24 and 52: • Leptin • LDL particle • Homocystein • Apo A1/B • HbA1c
Endocrine at screening only		Serology	Pregnancy
Hemoglobin A1c TSH FSH (for women only)	Lipid profile (fasting): Triglycerides Cholesterol and its subfractions (high-density lipoprotein [HDL] and low-density lipoprotein [LDL])	Hepatitis BsAg and core Ab (if positive core Ab, then reflex Hep B DNA) Hepatitis C Ab (if positive, then reflex HCV RNA) HIV	In females of childbearing potential: Serum β-hCG (Screening and if positive urine β-hCG) Urine β-hCG (all other visits) [†]

* vfpBMC and Leukocyte subsets US and Canada only.

† During the periods where study visits are every 6-8 weeks, women should continue to have pregnancy tests every 4 weeks, using home pregnancy urine tests, that will be provided to them. The site will call the subject every 4 weeks to obtain results of these pregnancy tests and will record the information in the source documents and CRF.

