7.2. Laboratory Evaluations

Laboratory data collected during the study will be analyzed and summarized using both quantitative and qualitative methods. Summaries of laboratory data will be provided for the Safety Analysis Set and will include data collected up to the last dose of any study drug plus 30 days for subjects who have permanently discontinued study drug, or all available data at the time of the database snapshot for subjects who were ongoing at the time of an interim analysis. The analysis will be based on values reported in conventional units. When values are below the LOQ, they will be listed as such, and the closest imputed value will be used for the purpose of calculating summary statistics as specified in Section 3.7.

A baseline laboratory value will be defined as the last nonmissing measurement obtained on or prior to the date/time of first dose of any study drug.

For placebo subjects who were then re-randomized, the baseline laboratory value for the re-randomization period will be the last available measurement obtained on or prior to the date/time of first dose of filgotinib. The lab abnormalities after the first dose of filgotinib will be assessed from the baseline of the re-randomization period.

A by-subject listing for laboratory test results will be provided by subject ID number and visit in chronological order for hematology, serum chemistry, and urinalysis separately. Values falling outside of the relevant reference range and/or having a severity grade of 1 or higher on the CTCAE severity grade will be flagged in the data listings, as appropriate.

No formal statistical testing is planned.

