7.2.1. Summaries of Numeric Laboratory Results

Descriptive statistics of Baseline values, values at each postbaseline visit and change from Baseline at each postbaseline visit will be provided by treatment group for the following laboratory tests:

- Hematology
 - Hematocrit
 - Hemoglobin
 - Platelet count
 - Red blood cell count
 - White blood cell (WBC) count
 - Mean corpuscular volume
 - Lymphocytes

- Monocytes
- Neutrophils
- Eosinophils
- Basophils
- Chemistry
 - Alanine aminotransferase (ALT)
 - Aspartate aminotransferase (AST)
 - Alkaline phosphatase (ALP)
 - Total bilirubin
 - Serum creatinine
 - Creatinine clearance by Cockcroft-Gault formula
 - Creatinine phosphokinase (CPK)
 - Glucose
- Lipid
 - Triglycerides
 - Total cholesterol
 - HDL
 - LDL
 - LDL/HDL ratio

Change from baseline to a postbaseline visit will be defined as the visit value minus the baseline value. The mean, median, Q1, Q3, minimum, and maximum values will be displayed to the reported number of digits; SD values will be displayed to the reported number of digits plus 1.

Median (Q1, Q3) of the observed values for the laboratory tests specified above will be plotted using a line plot by treatment group and visit.

In the case of multiple values in an analysis window, data will be selected for analysis as described in Section 3.8.3.

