7.2.2.1. Treatment-Emergent Laboratory Abnormalities

Treatment-emergent laboratory abnormalities are defined as values that increase at least 1 toxicity grade from baseline at any postbaseline time point, up to and including the date of last dose of any study drug plus 30 days for subjects who permanently discontinued study drug, or the last available date in the database snapshot for subjects who were still on treatment at the time of an interim analysis.

For placebo subjects who were then re-randomized, treatment-emergent laboratory abnormalities of placebo period are defined as values that increase at least 1 toxicity grade from the baseline at any postbaseline time point, up to and including the first dose date of filgotinib. Treatment-emergent laboratory abnormalities of re-randomized period are defined as values that increase at least 1 toxicity grade from the new baseline after Week 24 at any postbaseline time point, up to and including the date of last dose of any study drug plus 30 days, or the last available date in the database snapshot for subjects who were still on treatment at the time of an interim analysis.

Placebo subjects who were not re-randomized have treatment-emergent laboratory abnormalities in the placebo period which are defined as values that increase 1 toxicity grade from the baseline at any postbaseline time point, up to and including the date of last dose of any study drug plus 30 days.

If the relevant baseline laboratory value is missing, any abnormality of at least Grade 1 observed within the time frame specified above will be considered treatment emergent.

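### SAP 7.2.1 and 7.2.2.1 compare every follow-up glucose value with a normally fasting baseline, although 10 of 13 on-treatment samples need not be fasting, so within-arm change and any-visit incidence can reflect meals as well as drug

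*Protocol*

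**What the plan says.** Protocol 6.7.4 sets the fasting rule: "Subjects only need to be fasted at days were lipid profiling is scheduled". The Day 1 blood draws in Protocol 6.2.2 include both chemistry and the item that begins "Lipid profile (fasting". For the later visits, Protocol 6.4 lists "Lipid profile (fasting) at Weeks 12 and 24", and Protocol 6.5 adds a fasting lipid profile at Week 52/ET. The Protocol Appendix 2 table agrees. Its row "Hematology and Chemistry" is marked at every visit from Screening to Post Treatment Week 4.

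Protocol Appendix 6 places glucose in the chemistry panel ("Serum creatinine Glucose Phosphorus"). Only the lipid profile carries a fasting label there.

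Under SAP 7.2 the laboratory baseline is "defined as the last nonmissing measurement obtained on or prior to the date/time of first dose of any study drug". Placebo subjects who are re-randomized get a new baseline, the last value up to their first filgotinib dose. SAP 7.2.1 includes glucose in its list of tests and says that "values at each postbaseline visit and change from Baseline at each postbaseline visit will be provided by treatment group". SAP 7.2.2.1 defines treatment-emergent abnormalities as "values that increase at least 1 toxicity grade from baseline at any postbaseline time point", with follow-up running to 30 days past the final dose. None of the SAP laboratory sections records, separates or adjusts for fasting status. SAP 7.2 plans no formal test of laboratory data.

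**The concern.** A change from baseline is interpretable when both values are taken under the same conditions. Here the baseline is normally fasting and most follow-up values carry no fasting requirement. If some subjects eat before those visits, mean glucose change could rise at those visits and drop back at Weeks 12, 24 and 52 without any drug effect. A rule that flags a rise at any visit also gives each unfasted sample another chance to produce a meal-driven flag.

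Readers will use this table. HbA1c is scheduled at Screening only, except at carotid-imaging sites (Protocol Appendices 2 and 6), so elsewhere serum glucose is the only scheduled blood measure of glycaemia on treatment. Protocol 5.5 allows well-controlled diabetes and low-dose oral steroids. Protocol 7.5.3 already recognizes that fasting status matters, since it cites a nonfasting triglyceride rise as an example of a clinically non-significant Grade 4 result. The SAP makes no such distinction for glucose.

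**Working it through.** **1. Count of samples** (Protocol Appendix 2, cross-checked with 6.2.2, 6.4 and 6.5). On-treatment chemistry visits after Day 1 are Weeks 2, 4, 8, 12, 14, 16, 20, 24, 26, 30, 36, 44 and 52. Those with a fasting lipid profile are Weeks 12, 24 and 52.

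| Period | Chemistry draws | With fasting lipids | Fasting not required |
|---|---|---|---|
| Week 2 to Week 24 | 8 | 2 | 6 |
| After Week 24 | 5 | 1 | 4 |
| All on-treatment | 13 | 3 | 10 (10/13 = 77%) |

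The Post Treatment Week 4 draw has no lipid profile and can fall within 30 days of the last dose. Including it, 11 of 14 draws need not be fasting.

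**2. Which baseline applies.** Day 1 chemistry is drawn before dosing on a fasting-lipid day, so the SAP baseline is normally fasting. If Day 1 is missing, the baseline falls back to Screening, which has no lipid profile. For re-randomized placebo subjects the new baseline is normally the fasting Week 24 sample, and 4 of their 5 later on-treatment draws need not be fasting.

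**3. What is compared with what.** At Weeks 12, 24 and 52, change is fasting minus fasting. At the other ten visits it is a value of unknown fasting status minus a fasting value. The any-visit grade rule pools both kinds.

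**4. How an any-visit rule accumulates (illustration only).** Assume no drug effect, independent visits, and a chance q that an unfasted sample shows a meal-driven rise of at least one grade. Over k such samples the chance of at least one flag is 1 − (1 − q)^k. The documents give no value for q, so a range is shown.

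| q | k = 6 (to Week 24) | k = 10 (to Week 52) |
|---|---|---|
| 1% | 1 − 0.99^6 = 5.9% | 1 − 0.99^10 = 9.6% |
| 3% | 1 − 0.97^6 = 16.7% | 1 − 0.97^10 = 26.3% |
| 5% | 1 − 0.95^6 = 26.5% | 1 − 0.95^10 = 40.1% |

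The two columns also show that 52-week incidence in one arm should not be set against the placebo period in another, because the number of unfasted samples differs.

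**5. Why analysis windows cannot identify fasting draws.** An ET visit includes fasting lipids, but SAP Table 3-1 assigns chemistry by study day. For a subject not switched from placebo, ET on Day 250 puts the chemistry in the Week 36 window (Days 233 to 281). The lipid sample from the same visit goes to the Week 24 lipid window in Table 3-3 (Days 128 to 267). A flag based on windows would miss that fasting glucose.

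**The case against.** The case for leaving the SAP alone has several sound parts.

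- **Comparison between arms.** A reader might infer that the filgotinib-versus-placebo or filgotinib-versus-adalimumab glucose comparison is biased. The documents do not support that. All arms follow one blinded visit schedule, so any meal effect falls on them alike in the same period. Extra noise and possible dilution remain.
- **Actual fasting.** A reader might also infer that the ten other samples were non-fasting and that most subjects will be flagged. The plan says only that fasting was not required. How many subjects ate is unknown.
- **Grading.** CTCAE v4.03 is linked, not printed, and SAP 7.2.2 does not name glucose among the graded tests. The size of any inflation in grades cannot be derived from the documents.
- **Existing rows.** The planned by-visit table already contains the fasting-to-fasting changes at Weeks 12, 24 and 52. They are simply not distinguished from the rest.
- **Cost of restricting to fasting draws.** Grading only those draws would discard 10 of 13 samples, including Weeks 2, 4 and 8, and need not sharpen the contrast. Take an illustration with every input assumed: fasting mean 92 mg/dL, between-subject SD 8, within-subject SD 6, meal shift +5 with SD 10 at all ten visits, upper limit 110, drug effect +4 mg/dL. Three fasting samples give about 6% v 14% exceeding the limit (8 points); the planned mix gives about 67% v 80% (13 points). With a limit of 100, or a larger meal shift, fasting samples do better. The any-visit summary should therefore stay.
- **Importance.** The data are descriptive, with no formal test, and glucose is not among the laboratory evaluations of special interest in SAP 7.2.3.

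These points limit the consequence and shape the remedy. They do not make a fasting baseline comparable with an unlabelled follow-up value.

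**Conclusion.** The point holds for two outputs: within-arm glucose change at the ten visits without a lipid profile, and the absolute any-visit incidence of treatment-emergent high glucose. Both can mix meal and drug effects, and nothing in the SAP lets a reader tell them apart. The same applies to re-randomized placebo subjects after Week 24.

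It does not extend to a systematic bias between arms over the same period, nor to any efficacy result, alpha or power figure. The counts (10 of 13, and 6 of 8 to Week 24) come directly from the schedule. The size of the effect is not known, and the percentages above are illustrations under assumed inputs. The conclusion rests on fasting instructions being followed on lipid days and on at least some subjects eating before other visits. Severity: minor, in a descriptive safety table.

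**What to change.** In SAP 7.2.1, report glucose change from baseline for the fasting draws only, meaning those taken with a lipid profile (Weeks 12, 24 and 52/ET). Show glucose at the other visits separately as observed values, labelled *fasting not required*.

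In SAP 7.2.2, add a treatment-emergent high-glucose summary restricted to fasting draws. Keep the existing any-visit summary, including Grade 3 or higher and marked abnormalities, and label it as mixed fasting status, so that no safety signal is dropped.

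Identify a fasting draw by a lipid sample collected at the same visit, not by analysis window. This flag still reflects the requirement to fast and not confirmed fasting, which a footnote should say.

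The cost is SAP wording, one derived flag and one extra table, with fewer visits in the glucose change table. No new data or visits are needed.
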